CASE COMPREHENSIVE CANCER CENTER

STUDY NUMBER: CASE 5Y14

STUDY TITLE: Evaluation of Bone Metastases with Dual Energy CT

PRINCIPAL INVESTIGATORS:

[name]
Imaging Institute
Cleveland Clinic
[name]
[name]
[contact]

CO- INVESTIGATORS:

[name]
Imaging Institute
Cleveland Clinic
[name]
[name]
[contact]

[name]
Imaging Institute
Cleveland Clinic
[name]
[name]
[contact]

[name]
Quantitative Health Sciences
Cleveland Clinic
[name]
[name]
[contact]

[name]
Imaging Institute
Cleveland Clinic
[name]
[name]
[contact]

[name]
Solid Tumor Oncology
Cleveland Clinic
[name]
[name]
[contact]

STATISTICIAN: [name]
[contact]

SPONSOR: N/A

CLINICAL FACILITY: Cleveland Clinic

APPROVALS: Protocol Review and Monitoring Committee: Pending
Cleveland Clinic IRB: Pending

STUDY COORDINATOR: Imaging Institute
Cleveland Clinic

DEPARTMENT HEAD: [name]
Imaging Institute
Cleveland Clinic
[name]
[name]
[contact]

Abstract

Computed tomography (CT) scans are routinely used in the evaluation of oncologic patients for initial diagnosis and subsequent disease staging. Detection of bone metastasis on standard CT, however, is limited in sensitivity, particularly in case of osteolytic intramedullary lesions [1]. Recent studies have shown the ability to detect bone marrow edema using CT with the use of a virtual non-calcium (VNC) dual energy CT (DECT) technique[2, 3]. Because bone marrow edema is similar in composition to intramedullary bone metastases (i.e. both are of soft tissue composition as opposed to calcium or fat), VNC DECT may also be helpful in the detection of bone marrow metastasis. Cancer patients obtaining a Positron Emission Tomography (PET) CT and a separate diagnostic CT scan as part of their routine clinical care will be enrolled into the study. The diagnostic CT scan will be performed on a DECT scanner and the images will be reconstructed as SECT images for routine clinical interpretation as well as VNC DECT images. The SECT images alone will be evaluated and scored, and then the VNC DECT images will be added to the SECT images for a second evaluation (consecutive reading session). Multiple readers blinded to the PET-CT findings for detection of bony metastatic disease will participate.

Primary Aims

- 1) Compare the accuracy of SECT with VNC DECT to standard SECT alone in the detection of metastatic bone lesions using PET-CT as the reference standard.

Hypothesis

The addition of VNC DECT to SECT will be more accurate in the detection of metastatic bone marrow lesions compared to SECT alone.

Introduction

Significance and Rationale

Bone is the most common site of metastatic disease.[4] Nearly 300,000 US adults are estimated to be living with metastatic bone disease.[5] Nearly two thirds of bone metastases occur in patients with breast, prostate, and lung cancer.[5] Bone metastases can present as predominantly sclerotic, lytic or mixed sclerotic and lytic lesions.

CT is the primary imaging modality utilized for the detection and staging of metastatic cancer because of its ability to evaluate a wide range of tissues in a short time and availability in many locations. The sensitivity of CT in detection of bone metastases is, however, limited with a recent meta-analysis reporting a pooled sensitivity of 73% compared to PET (pooled sensitivity 90%) and MRI (pooled sensitivity 90%)[1]. Detection of osteolytic lesions that are intra-medullary without cortical or soft tissue involvement is especially challenging on CT. These lesions most frequently occur in

patients with breast and lung cancer as well as patients with multiple myeloma and lymphoma. The primary difficulty of identifying intramedullary bone marrow lesions with conventional CT is the ability to visually discriminate the lesion which is of soft tissue composition through the trabecular bone which is composed of calcium. DECT with the use of a virtual non-calcium technique provides the ability to remove calcium and thereby the trabecular bone from the image and at least theoretically improve visualization of the underlying marrow elements composed of soft tissue and fat.

Although DECT has been available for several decades, it has not been widely used in clinical practice because of technical limitations and radiation dose concerns.[6] Recent second generation of DECT scanners from several vendors now have addressed many of the prior limitations allowing DECT scans to be performed with dose and image quality comparable to SECT scans.[7-9] Schenkle et al. showed that there is no significant difference in image noise for chest CT using DECT compared to SECT when performed with the same dose and the contrast to noise ratio can be doubled with optimized DECT protocols.[7] They concluded that CT can be routinely performed in dual energy mode without additional dose or compromises in image quality. Similarly, Purysko et al. showed that by adjusting the tube current (mA) at the scanner console to match the radiation output (CTDIvol) from a single energy CT (SECT), DECT of the abdomen can be performed without radiation dose penalty to patients. Using this technique in a cohort of patients undergoing single energy (SECT) and dual energy CT (DECT) in different occasions, DECT exams achieved similar image quality with similar or lower radiation dose compared to SECT. [10] The advantage of DECT is ability to separate tissues by material composition rather than simply by attenuation as in SECT. This is possible because change in attenuation of different materials between the two energies is related to the individual properties of the material (primarily its atomic number). As a general rule of thumb, as the difference in atomic numbers between the materials increases, the ability to separate the materials improves. DECT using this technique is currently being used in routine clinical practice in a number of applications such as multiphasic vascular, liver and kidney studies.[11, 12] For intramedullary bone, this same technique is modified to separate or “decompose” each voxel into fat, soft tissue (hematopoietic marrow), and calcium (trabecular bone). After the voxel is decomposed into those 3 materials, the calcium can be subtracted from the voxel creating a “virtual non-calcium” (VNC) image and removing the trabecular bone from the medullary space.[2]

Relevant literatures

There have been no studies to date showing the benefit of VNC DECT for the evaluation of bone metastases. Recent studies have, however, demonstrated the ability to visualize bone marrow edema with CT by using a VNC post processing technique of a DECT scan without increased radiation dose.[2, 3, 13] Pache et al. showed that VNC DECT can be used to identify bone marrow edema in the knee in a study of 21 patients with acute knee trauma.[2] The same group also showed that the detectability of the bone marrow edema is no different when using a dose equivalent to SECT and concluded that DECT can

provide additional information compared to SECT without additional radiation dose.[3] More recently, Bierry et al. showed that bone marrow edema in vertebral compression fractures can be accurately detected using VNC DECT.[13] Our hypothesis is that the same principle which allows visualization of bone marrow edema should also allow visualization of bone marrow metastases using a VNC technique with subtraction of trabecular bone. Preliminary work performed by one of the investigators (JP) has demonstrated the ability to identify bone marrow metastasis using a trabecular bone subtraction algorithm with SECT.

Methods

Data Collection

A subset of cancer patients being imaged with PET/CT for diagnosis and/or staging of disease at our institution also undergo a diagnostic CT scan as part of the clinical workup at the same time or within a short period of time. This subset of patients will be divided into 2 cohorts: patients with bone metastases on PET/CT and patients without bone metastases on PET/CT. 30 patients with bone metastases and 15 patients without bone metastases will be enrolled into the study. To be included in the study, the time between the diagnostic CT and PET/CT will be no more than 30 days with no intervening treatment to ensure that any differences found between the exams are related to imaging technique and not a change in disease. Minors (age < 18 years) will be excluded from the study. In order to maximize recruitment and generalizability of study results, all cancer types and both newly diagnosed and previously treated patients will be included. However, the vast majority of the patients that are imaged with PETCT and diagnostic CT are lymphoma patients.

All study patients will undergo a dose-matched DECT (140 kVp and 100 kVp) scan instead of a standard 120 kVp SECT for their diagnostic CT. All scans will be performed on a single second-generation DECT scanner (Somatom Definition Flash, Siemens, Forchheim, Germany). A dual energy CT protocol using 140 kVp with Sn filter for the high energy beam (tube B) and 100 kVp for the low energy beam (tube A) will be performed with ~1.3 (tube A/tube B) ratio of tube currents. Multiplanar reformations will be done in 1mm – 3mm thick slices using a soft reconstruction kernel. To ensure that the radiation dose of the DECT will be no higher than the standard SECT protocols (Appendix 1), the CT dose index (CTDvol) which measures the radiation output of the CT tube will be calculated for the SECT scan in each patient and the DECT tube currents will be adjusted to match this CTDvol. CT scans will be performed as routine diagnostic scans with administration of intravenous contrast and with or without oral contrast depending on the clinical indication. Established institutional guidelines will be followed for the administration of intravenous and oral contrast. (Appendix 2 and Appendix 3) . Linearly mixed images from the DECT will serve as the SECT equivalent images for clinical interpretation. These images are generated by combining the data from both energies (in other words, all the radiation dose will be used to generate these images). Post processed VNC DECT images will also be generated. 8 readers will evaluate the anonymized images in a single reading session. The SECT equivalent images will first

Each patient will be evaluated and scored at approximately 46 separate locations (12 pairs of ribs, 12 thoracic vertebra, 5 lumbar vertebra, sacrum, right and left hemipelvis, and right and left scapula). For each location, the readers will mark the presence or absence of lesions, the number of lesions and their confidence in the presence of one or more lesions in that particular anatomic location (using a 0-100 point confidence scale). Each location will be correlated with PETCT which will serve as the reference standard. Previous studies have shown PET to be the most accurate imaging technique to detect bone metastases and superior to nuclear medicine bone scintigraphy. [1] PET is still an imperfect gold standard. Unfortunately, only histopathology of each lesion would serve as a better gold standard which would not be feasible or ethical. Accuracy will be measured using nonparametric estimates of the area under the receiver operating characteristic (ROC) curve using methods for clustered data (i.e. multiple locations per patient) [14]. ROC area estimates will be constructed for each reader for both SECT alone and DECT as an adjunct to SECT. For each reader, the ROC areas of SECT and DECT plus SECT will be compared using a Wald test [14]; a significance level of 0.05 will be used.

ANOVA methods for multiple-reader ROC studies will be used to test the null hypothesis that the readers' mean ROC area with DECT as an adjunct to SECT is the same as the readers' mean ROC area with SECT alone [15]. A significance level of 0.05 will be used. A 95% confidence interval for the difference in ROC areas will be constructed.

Sample Size Considerations

Methods for determining sample size for multi-reader CAD studies was used [16]. The following assumptions were made for sample size calculation:

1. Based on previous work by Yang et al [1], we expect readers to have a high ROC area with SECT. Thus, we used an estimate of 0.90 as the ROC area with SECT.
2. We expect that DECT will increase readers' sensitivity by 0.10 or more, with little to no effect on specificity. Thus, we assumed that the ROC area with DECT will be 0.05 greater than with SECT alone.

Patients with metastatic disease will have, on average, 2 lesions [1],

The formula for determining sample size for MRMC studies [17] is:

$$\text{Power} = 1 - F(f_c; 1, df_1, \lambda) \quad [1]$$

where $F(f_c; 1, df_1, \lambda)$ is the distribution function of the test statistic F under the alternative hypothesis and $f_c = F^{-1}(1-\alpha; 1, df_1)$, where df_1 is $(J-1)$ and

$$\lambda = [J ((\mu_{QT} - \mu_{HH}) + 0.05)^2] / [2 \{ \sigma_b^2 (1 - r_b) + \sigma_\varepsilon^2 [(1 - r_1) + (J - 1)(r_2 - r_3)] \}]$$

is the noncentrality parameter of the noncentral F distribution, J is the total number of readers in the study, σ_b^2 is the variability between readers, r_b is the correlation between accuracies when the same readers evaluate subjects using different tests, σ_ε^2 is the variability due to different subject samples, r_1 is the correlation between accuracies when the same subjects are evaluated by the same reader using different tests, r_2 is the correlation between accuracies when the same subjects are evaluated by different readers using the same tests, and r_3 is the correlation between accuracies when the same subjects are evaluated by different readers using different tests. We used estimates of σ_b^2 , r_b , r_1 , r_2 , and r_3 from prior studies [16]. Note that σ_ε^2 is a function of the *effective* sample size, which we estimate as: # patients x 46 locations / design effect, where the design effect is $1 + (s-1)r$ [16], where $s=46$ locations and r is the correlation between locations which we assume to be 0.5 for locations with mets and 0.2 for locations without mets [16].

From equation 1, we estimate that a study with 8 readers and 30 patients with bone metastases and 15 patients without metastatic disease will provide 84% power to detect a difference in ROC area of 0.05 or larger.

Informed Consent

A waiver of informed consent is being requested as participation in this study involves no more than minimal risk to the patient. DECT is FDA approved and used in routine clinical practice at many centers including the Cleveland Clinic for other purposes such as vascular imaging. Patients participating in this study will not receive additional CT scans or radiation. Dose and image quality of the scans will be equivalent to standard SECT scans. All the imaging studies that will be evaluated as part of this protocol will be obtained as a part of the routine clinical care of the patient. Eligible patients will be provided an information sheet (Appendix 4) explaining the study prior to their CT scans and participation in the study will be voluntary. Since all patients will undergo PETCT which will serve as the truth for the presence or absence of bone marrow metastasis, DECT will never by definition reveal lesions not detected by PETCT and any advantage of DECT over SECT in the detection of bone metastases will not directly benefit patients in the study.

To increase recruitment of patients with bone metastases, we would like to add an additional procedure as an amendment to the protocol. Patients of study co-investigators or licensed independent practitioners working with the co-investigators, with known bone

metastases who will be getting a routine clinical CT scan, will be asked to participate in the study by the ordering clinician. Patients will be provided with the patient information sheet (Appendix 4). If they volunteer to participate in the study, the clinical CT scan will be performed using a dual energy technique as stated in the protocol. In these patients, follow-up CT scans performed as part of routine clinical care will be used to confirm the presence or absence of any additional lesions detected using the dual energy CT technique. As before, enrolled patients will not receive any additional CT scans or any additional radiation exposure by participating in this study.

Confidentiality Assurances

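### The printed power calculation conflicts with the plan's own assumptions in two places (a stray + 0.05, and all 46 locations of a metastatic patient counted as positive), so the 84% cannot be verified as printed

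*Combined protocol and SAP*

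**What the plan says.** All references are to the combined protocol and SAP.

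- **Test (Data Analysis).** The null is that the readers' mean "ROC area with DECT as an adjunct to SECT is the same as" the mean area with SECT alone. On error rate and estimation: "A significance level of 0.05 will be used. A 95% confidence interval for the difference in ROC areas will be constructed". No margin is given anywhere.
- **Effect (Sample Size Considerations).** The SECT area is taken as 0.90, and "we assumed that the ROC area with DECT will be 0.05 greater than with SECT alone".
- **Lesion count (same section).** "Patients with metastatic disease will have, on average, 2 lesions".
- **Noncentrality (same section).** λ has numerator "J ((\mu_{QT} - \mu_{HH}) + 0.05)^2" and denominator 2{σ_b²(1 − r_b) + σ_ε²[(1 − r_1) + (J − 1)(r_2 − r_3)]}. The reader count, variances and correlations are defined. The two means and the added 0.05 are not.
- **Effective sample size (same section).** σ_ε² depends on an effective count, given as the number of "patients x 46 locations / design effect, where the design effect is" 1 + (s − 1)r, with s = 46 and r = 0.5 for locations with metastases or 0.2 for locations without.
- **Result (same section).** "From equation 1, we estimate that a study with 8 readers", 30 patients with metastases and 15 without "will provide 84% power to detect a difference in ROC area of 0.05 or larger".

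**The concern.** For a test of zero difference, λ must be zero when the two areas are equal. As printed, it is zero at a difference of −0.05 and positive at equality.

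The effective-size rule raises a separate question. It multiplies patients by 46 and applies the correlation for locations with metastases. For the 30 metastatic patients this makes every location a positive one, against the plan's own average of 2 lesions. The number of effective positives drives σ_ε², so an overstated count overstates power.

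The 84% is the only stated justification for 8 readers and 45 patients. What is at stake is whether that figure is supported. The null, the significance level, the confidence interval and the planned analysis do not use this formula.

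**Working it through.** **Inputs from the plan:** J = 8, F test on 1 and 7 df, α = 0.05, difference d = 0.05, 30 + 15 patients, 46 locations, r = 0.5 or 0.2, 2 lesions per metastatic patient. **Not printed:** σ_b², r_b, r_1, r_2, r_3, σ_ε², and the split into positive and negative locations. The 84% therefore cannot be reproduced directly, and I worked back from it.

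**1. What 84% requires.** The critical value is F⁻¹(0.95; 1, 7) = 5.591. Solving 1 − F(5.591; 1, 7, λ) = 0.84 gives λ = 11.916. Write D for the term in braces, so D = J d²/(2λ). With d = 0.05, D = 8 × 0.0025/(2 × 11.916) = 0.000839.

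**2. The numerator.** With the assumed 0.05 in the bracket, the squared term is (0.05 + 0.05)² = 0.0100 instead of 0.0025, a factor of 4. If the bracket was set to 0 and the added 0.05 is the assumed gain, the term is 0.0025, as the stated test requires.

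**3. Which is more likely?** I assumed the Hanley-McNeil variance at area 0.90 with 69 effective negatives, r_1 of 0.4–0.7, r_2 − r_3 of 0–0.10, and a reader term σ_b²(1 − r_b) of 0–0.0004.

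| Effective positives | Power, 0.05 entered once | Power, 0.05 entered twice |
|---|---|---|
| 58.7 | 60% to >99.9% | 99% or more |
| 40 | 50% to 99% | 97% or more |

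On these inputs 84% is attainable with single entry, while double entry would have given a figure close to 100%.

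**4. Effective counts.**
- Design effects at s = 46: 1 + 45 × 0.5 = 23.5 and 1 + 45 × 0.2 = 10.
- Literal rule: positives 30 × 46/23.5 = 1380/23.5 = 58.7; negatives 15 × 46/10 = 69.
- With 2 lesions per metastatic patient, each in its own location: 60 positives, design effect 1 + 1 × 0.5 = 1.5, effective 60/1.5 = 40.
- Negatives are then 69, or (690 + 30 × 44)/10 = 201 if the lesion-free locations of metastatic patients are included.

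**5. Effect on σ_ε² (assumed Hanley-McNeil form).** Variance = [A(1 − A) + (n₁ − 1)(P₁ − A²) + (n₀ − 1)(P₂ − A²)]/(n₁n₀), where n₁ and n₀ are effective positives and negatives, P₁ = A/(2 − A) and P₂ = 2A²/(1 + A). At A = 0.90, P₁ − A² = 0.00818 and P₂ − A² = 0.04263.
- 58.7 and 69: (0.09 + 57.7 × 0.00818 + 68 × 0.04263)/(58.7 × 69) = 0.000854.
- 40 and 69: (0.09 + 39 × 0.00818 + 68 × 0.04263)/2760 = 0.001199, ratio 1.403.
- 40 and 201: (0.09 + 39 × 0.00818 + 200 × 0.04263)/8040 = 0.001111, ratio 1.301.

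At A = 0.95 the same steps give 0.000432, 0.000619 (ratio 1.433) and 0.000593 (ratio 1.371).

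**6. Effect on power.** Suppose 84% came from 58.7 and 69 with 0.05 entered once, so D = 0.000839. Let a share f of D be the reader term, which does not depend on location counts, and hold the correlations fixed. With R the variance ratio, D is multiplied by f + (1 − f)R, and λ = 11.916/[f + (1 − f)R].

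| A | Negatives | R | λ, f = 0 | Power, f = 0 | λ, f = 0.5 | Power, f = 0.5 |
|---|---|---|---|---|---|---|
| 0.90 | 69 | 1.403 | 8.49 | 71% | 9.92 | 77% |
| 0.90 | 201 | 1.301 | 9.16 | 74% | 10.36 | 79% |
| 0.95 | 69 | 1.433 | 8.32 | 70% | 9.80 | 77% |
| 0.95 | 201 | 1.371 | 8.69 | 72% | 10.05 | 78% |

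**The case against.** The strongest defence is that the formula is mistyped but was correctly used. If the bracket holds the null difference of 0, the printed numerator equals J(0.05)². The labels on the two means may be PDF reading errors, the effect is stated consistently as 0.05, and step 3 favours single entry. This stands: the added 0.05 is a fault in the written rule and is not evidence against the 84%.

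The unlisted variance and correlation values are cited to a published source. Leaving them out is missing detail, not an error.

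On the counts, the sponsor may have used lesion-based numbers despite the printed rule, in which case nothing is lost. Patients may also have more than 2 positive locations. With m per patient, the effective number is 30m/[1 + 0.5(m − 1)], which rises from 40 at m = 2 to 50 at m = 5 and 58.7 at m = 46. The possible loss is therefore limited. Neither argument removes the conflict, because the plan states an average of 2 lesions and prints a rule that does not use it.

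Three stronger readings are tempting, and the documents support none of them.
- A reader might infer that true power is 32%. That follows only if 84% was obtained with 0.05 counted twice (λ = 11.916/4 = 2.98), which step 3 makes unlikely.
- A reader might divide 60 positives by 23.5 and infer 2.6 effective positives. The plan pairs s = 46 with 46 locations per patient and never applies that design effect to 2 locations.
- A reader might take the shift as a hidden non-inferiority margin of 0.05. The stated null is equality and no margin appears.

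**Conclusion.** The point holds in this form: two printed rules disagree with the plan's own test and assumptions, so the 84% cannot be verified as printed. It is not shown to be wrong.

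The numerator is wrong as written, by a factor of 4 at the assumed difference, but is probably a notation error with no effect on the 84%. The location count is the more consequential conflict. If the literal rule was used, power for a 0.05 difference is about 70–79% instead of 84%. That range assumes Hanley-McNeil variances at areas of 0.90–0.95, a reader term of 0–50% of D, unchanged correlations, 69–201 effective negatives, and each lesion in its own location. A larger reader share would make the loss smaller.

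**What to change.** Under Sample Size Considerations:

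1. Replace the numerator with J(μ_SECT+VNC − μ_SECT)², define both means, and enter 0.05 once.
2. Base σ_ε² on the expected numbers of positive and negative locations, with design effects that match the locations per patient of each type. Say how the average of 2 lesions enters and whether lesion-free locations of metastatic patients count as negatives.
3. List the values actually used for σ_b², r_b, r_1, r_2, r_3 and σ_ε².
4. Rerun equation 1 for 8 readers and 30 + 15 patients. Then confirm 84%, or restate the power or the detectable difference.

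The cost is a text edit and one recalculation. No patients or readers are added, and the analysis does not change. The stated power may become less favourable.
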